3.2 Secondary Objectives

- 3.2.1** To assess inter-observer agreement for the detection of any varices and high-risk varices on dual energy CT.
- 3.2.2** To compare the accuracy of grade of varices on CT to grade of varices on endoscopy for predicting gastroesophageal variceal bleeding at 2 years.
- 3.2.3** To develop and compare the accuracy of multivariate statistical models designed to predict 2-year risk of bleeding gastroesophageal varices, both without and with dual energy CT findings.
- 3.2.4** To predict 2-year liver-related events using the variceal grade on DECT, LSN score and MELD score.

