Study participants will undergo DECT imaging of the liver in the late arterial and in the portal venous phases. The late arterial phase will be performed with bolus tracking and occur 20 seconds after triggering. The portal venous phase will also be performed with bolus tracking and occur 40 seconds after triggering. Both phases will utilize our standard-of-care DECT image acquisition protocol. Imaging will be performed per standard of care, with the patient in the supine position with arms above the head. No oral contrast will be administered. Noncontrast and delayed phase imaging will not be performed to reduce the radiation dose.

11.3.2 DECT Image Evaluation:

The DECT images will be interpreted according to our standard of care with a dictated report by a board-certified abdominal radiologist. The radiologist interpreting the study will be asked to interpret the study using a structured reporting template that includes the grade of esophageal varices, presence or absence of other varices, presence or absence and stage of HCC, severity of ascites, and patency of liver vasculature. The structured report template is currently in use by multiple abdominal faculty and can be easily acquired by any abdominal radiologist at UAB through Powerscribe, our routine dictation reporting system.

Each DECT study will be de-identified per standard technique using OsiriX. A coded identifier will be applied to each image, and the images will be stored on OsiriX and on a secure password-restricted Server Message Block (SMB), a virtual hard drive established for Radiology Clinical Research that has restricted access to defined users. Study personnel will use the Liver Surface Nodularity (LSN) Software to measure the LSN score on all patients, while remaining blinded to the clinical data. [name] or [name] will review all of the exported images and confirm a satisfactory measurement for each patient, with revising of measurements that are not satisfactory.

11.3.3 Inter-observer Analysis:

After all patients are recruited (N=50), a designated co-investigator will set up reading session for the other radiology co-investigators (N=4 radiology residents and N=4 radiology faculty). A training video will be prepared and used to instruct the readers on how to view the images, conduct the reading sessions, and record the data in a REDCap.

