A combination of variceal grade on DECT, LSN score and MELD score will have equal or greater accuracy for predicting 2-year liver-related events than a combination of endoscopic findings and MELD score. This analysis will be exploratory in Aim 2.4, but a trend may be evident and justify further investigation. Competing risks analysis will be used to assess the association of variceal grade on DECT, LSN score and MELD scores with development of liver-related events, with specific attention to 2-year variceal bleeding events. Cumulative Incidence Function (CIF) will be used to estimate the marginal probability of a liver-related event as a function of its cause-specific probability and overall survival probability.

All analysis will be carried out using SAS v 9.4.

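### Aim 2.4 is a valid CT-package contrast, but with LSN on the DECT side only it cannot show whether a favourable trend comes from the DECT variceal grade

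*Combined protocol and SAP*

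**What the plan says.** Objective 3.2.4 is "To predict 2-year liver-related events using the variceal grade on DECT, LSN score and MELD score". It names no comparator. Section 13.2 supplies one. It states: "A combination of variceal grade on DECT, LSN score and MELD score will have equal or greater accuracy for predicting 2-year liver-related events than" the comparator. That comparator is worded "than a combination of endoscopic findings and MELD score". MELD is on both sides and LSN on one.

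On status and method, section 13.2 adds: "This analysis will be exploratory in Aim 2.4, but a trend may be evident and justify further investigation". It then says: "Competing risks analysis will be used to assess the association of variceal grade on DECT, LSN score and MELD scores with development of liver-related events". No accuracy measure, margin or test is given for this aim.

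LSN is described in section 11.3.2, under DECT image evaluation: "Study personnel will use the Liver Surface Nodularity (LSN) Software to measure the LSN score on all patients, while remaining blinded to the clinical data". It is therefore a CT-derived marker, and every participant will have it.

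Endoscopic findings are not defined for Aim 2.4. Section 11.2 has endoscopists record variceal grade, red wale or red spot sign, gastric varices, portal gastropathy and several other items.

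**The concern.** The contrast answers one question: does the CT package predict liver-related events as well as endoscopy, given MELD on both sides? It leaves a second question open: does the DECT variceal grade predict as well as the endoscopic one? A favourable result could come from the grade, from LSN, or from both.

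This matters because the study is about DECT for varices (section 3.1), and the plan gives the Aim 2.4 trend a use, namely to justify further work. If LSN drives the trend, the work to follow up is on LSN rather than on variceal grading by DECT. The planned comparison would not tell the investigators which.

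**Working it through.** **1. Is the separation made elsewhere?**

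- Objective 3.2.2 does set grade against grade, but for another outcome: "To compare the accuracy of grade of varices on CT to grade of varices on endoscopy for predicting gastroesophageal variceal bleeding at 2 years".
- Objective 3.2.3 compares models without and with DECT findings, again for variceal bleeding only.
- The Aim 2.3 text in section 13.2 extends to any hepatic complication and adjusts for covariates. The Aim 2.4 text lists grade, LSN and MELD in a competing-risks analysis. Both give associations. Neither gives the accuracy of DECT grade against endoscopic grade with the same companion markers.

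So no like-for-like accuracy comparison is planned for liver-related events.

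**2. Inputs.** The plan states no figure for Aim 2.4 that could be reproduced; its only power statement (section 13.1) concerns the primary aim. From the documents: N = 50 and a grade mix of 32/32/36% (section 13.1). Assumed: event rate, effect sizes, logistic models for two-year status, and apparent AUC as the accuracy measure. At a 30% event rate there are 0.30 × 50 = 15 events.

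**3. Large-sample AUCs, with sampling noise removed.** Settings: 30% events, independent predictors, log-odds per SD of 0.5 for MELD, 0.5 for endoscopic grade and 0.8 for LSN, and a DECT grade with no information (the limiting case).

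| Model | AUC |
|---|---|
| DECT grade + LSN + MELD | 0.722 |
| Endoscopic grade + MELD | 0.668 |
| DECT grade + MELD | 0.616 |
| Endoscopic grade + LSN + MELD | 0.753 |

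- As specified: 0.722 − 0.668 = +0.054, favouring DECT.
- LSN on neither side: 0.616 − 0.668 = −0.052.
- LSN on both sides: 0.722 − 0.753 = −0.031.
- Decomposition: LSN's increment is 0.722 − 0.616 = 0.106, and 0.106 − 0.052 = 0.054. LSN supplies all of the apparent advantage and offsets a deficit in the grade.

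**4. Trials of 50 patients.** A latent variceal severity S, MELD (M) and LSN (L) drive the event: logit P = a + 0.8·S + 0.6·M + b·L, with b = 0.5 to 0.7 and about 30% events. Endoscopic grade has latent correlation 0.85 with S. DECT grade has 0 or 0.5, so it is less informative than endoscopy. The table gives the share of trials in which the DECT side's apparent AUC is equal or better.

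| Endoscopy model | As specified | Like-for-like |
|---|---|---|
| Grade + MELD | 53-71% | 24-34% |
| Grade + two uninformative findings + MELD | 36-54% | 11-18% |

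In the first row, a half-informative DECT grade (correlation 0.5) gives 60-71% against 31-34%, so the result does not need a worthless grade. Setting low end against low end and high against high, the gaps are 53 − 24 = 29 and 71 − 34 = 37 points in the first row, and 36 − 11 = 25 and 54 − 18 = 36 in the second.

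**5. Sensitivity.** Now use independent predictors, an uninformative DECT grade and event rates of 20% to 40% (1,500 trials per setting, so a standard error of at most √(0.25/1500) ≈ 1.3 points).

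- Endoscopy log-odds 0.5, LSN 0.5 to 1.0: 59-87% as specified, 26-37% like-for-like.
- Endoscopy 0.8, LSN 0.8 to 1.0: 55-70% against 12-20%.
- LSN pure noise, endoscopy 0.5 or 0.8: 17-46% against 9-32%. If LSN does not predict, the DECT side usually loses even as specified.

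**6. Is the extra term itself an advantage?** With the two grades equally good and LSN pure noise, the DECT side is equal or better in 64% of trials, against 52% without LSN. Two uninformative findings added to the endoscopy model bring the 64% down to 42%. The direction depends on how endoscopic findings are defined.

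**The case against.** The strongest reply is that the plan makes no claim about the grade alone. Both objective 3.2.4 and the hypothesis name the combination. LSN comes from the CT, and a patient with endoscopy alone has no LSN score. Putting LSN on the endoscopy side tests endoscopy plus CT, which is a different question. If LSN truly predicts events and the CT package does better, the stated hypothesis is correct. This stands: the package contrast is legitimate and need not be demoted.

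A second reply is that a useless DECT grade would show up in the primary ROC analysis and the weighted kappa against endoscopy. This stands in part. Those analyses measure agreement with endoscopy, not prediction of events, and the attribution problem also appears with a half-informative grade.

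A third is weight: the last secondary objective of a 50-patient pilot, labelled exploratory, with no decision rule. This stands, and it sets the level of the recommendation.

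A reader might go further and infer that the comparison is biased towards DECT, because the DECT model has an extra fitted term assessed in the patients used to fit it. The documents do not support that. The endoscopic term is plural and undefined, section 11.2 records many candidate items, and two extra findings are enough to reverse the advantage.

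**Conclusion.** The point holds as one of attribution, not of validity. Aim 2.4 can show whether the CT package keeps pace with endoscopy. It cannot show whether the DECT variceal grade does, and nothing else in the plan does so for liver-related events on an accuracy scale.

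Under the assumptions in step 4, a DECT grade inferior to endoscopy still sits on the equal-or-better side in about 53-71% of trials, against 24-34% like-for-like; with a fuller endoscopy model, 36-54% against 11-18%. The size rests on an assumed event rate, on how predictive LSN is and on what counts as an endoscopic finding, none of which the documents give. It would be wrong to infer that a favourable trend is spurious: it may be a true property of the package. Because the aim is exploratory and the primary objective is untouched, this is an optional improvement.

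**What to change.** In section 13.2 (Aim 2.4):

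- Keep the package contrast as stated, and list which items make up the endoscopic findings.
- Add DECT grade + MELD against endoscopic grade + MELD, and the same pair with LSN on both sides.
- Report the increment from LSN separately.
- Name the accuracy measure, and give bootstrap optimism-corrected values for every model. The correction deals with overfitting only. It does not replace the matched models, since the reversal in step 3 is present in large samples.
- State that a trend will be attributed to DECT variceal grading only if the matched comparisons support it.

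The cost is SAP wording and a few extra model fits on data already being collected. The downside is a result that may look less favourable to DECT grading. The models should be fixed before outcomes are analysed, so that the choice of comparator is not open to selective reporting.

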13.2 Statistical analysis plan

Patient and imaging characteristics will be summarized and compared using appropriate summary statistics, e.g. mean and standard deviation for continuous variables, frequency and percentage for categorical variables, and extensive exploratory data analysis and data visualizations will be utilized to assess diagnostics, identify outliers, and validate assumptions.

Receiver operating characteristic (ROC) analysis will be used in Aim 1 to estimate the accuracy of DECT for differentiating no varices from any varices and for differentiating no and small varices from large varices in Aim 1. Sensitivity, specificity, accuracy, and AUC along with their two-sided 95% CI will be presented separately. The grade of varices (0, 1, 2) on DECT will be correlated with the grade of varices on endoscopy (0, 1, 2) using weighted Kappa coefficient for categorical data (Aim 2.2).

The MIXED effect model will be used in Aim 2.1 to estimate the ICC for the inter-observer agreement for the detection of any varices and high-risk varices on dual energy CT. Reader experience and subject will be the two random effects in the model used for interobserver variability. The intraclass correlation coefficient (ICC) will be defined as the ratio between subject variance and the sum of variances for subject, reader experience and error term. ICC values will be characterized as very poor (0 to <0.20), poor (0.20 to <0.40), moderate (0.40 to <0.60), good (0.60 to <0.80), and very good (0.80 to 1.00).

Time to development of bleeding varices (or hepatic event) will be modeled in Aim 2.3 using Cox proportional hazards models with clustered sandwich estimators to account for within and between cluster correlations. Cause specific proportional subhazards analysis while accounting for competing risks (e.g. gastroesophageal banding) and adjusting for covariates will be utilized to assess the association between endoscopic findings and DECT findings and time to developing individual vs. any hepatic complications.

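### Exploratory Aim 2.4 hypothesises a comparison of accuracy with endoscopy + MELD, but no analysis planned for the aim estimates that comparison

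*Combined protocol and SAP*

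**What the plan says.** Section 13.2 opens its Aim 2.4 paragraph with a comparative hypothesis. A combination of DECT grade, LSN score and MELD "will have equal or greater accuracy for predicting 2-year liver-related events than a combination of endoscopic findings and MELD score". It then sets the status of the aim: "This analysis will be exploratory in Aim 2.4, but a trend may be evident and justify further investigation".

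Two analyses are described for it:

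- "Competing risks analysis will be used to assess the association of variceal grade on DECT, LSN score and MELD scores", with liver-related events as the outcome and particular attention to variceal bleeding by 2 years.
- "Cumulative Incidence Function (CIF) will be used to estimate the marginal probability of a liver-related event".

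The matching objective, 3.2.4, names no comparator: "To predict 2-year liver-related events using the variceal grade on DECT, LSN score and MELD score".

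The neighbouring text comes close in three places:

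- Aim 2.3 in section 13.2 uses cause-specific models "to assess the association between endoscopic findings and DECT findings and time to developing individual vs. any hepatic complications".
- Objective 3.2.3 is "To develop and compare the accuracy of multivariate statistical models designed to predict 2-year risk of bleeding gastroesophageal varices", without and with DECT findings. Objective 3.2.2 compares CT grade with endoscopic grade, also for bleeding.
- AUC with a two-sided 95% CI is planned in section 13.2, but in the Aim 1 paragraph, for detecting varices against endoscopy.

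**The concern.** The hypothesis concerns the difference in accuracy between two sets of predictors at 2 years. A hazard ratio for DECT grade or LSN shows whether that variable is related to the event. A cumulative incidence curve shows how often the event occurs. Neither shows how well a combination separates patients who will have an event from those who will not, and neither says anything about the endoscopy + MELD combination, which is not fitted.

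DECT grade could therefore be clearly associated with events while the DECT combination predicts better than, as well as, or worse than endoscopy + MELD. The planned output would not distinguish these cases. At stake is the use the plan gives the aim, which is to decide whether a trend justifies further work. The trend of interest is a contrast with endoscopy, and no contrast is produced.

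**Working it through.** **1. The plan's own figure.** The only computed figure is the power for Aim 1 in section 13.1: above 95% for AUC 0.90 against 0.5, one-sided 0.05, with 34 patients with varices and 16 without. Hanley-McNeil standard errors are 0.0884 at AUC 0.5 and 0.0429 at 0.90. Then z = (0.40 − 1.645 × 0.0884) / 0.0429 = 5.9, so power exceeds 99.9% and the stated bound holds. It concerns detection of varices and carries no information about Aim 2.4.

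**2. What the hypothesis needs, against what is planned.**

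| Needed | Planned for Aim 2.4 | Nearest text elsewhere |
|---|---|---|
| Model for DECT grade + LSN + MELD | Yes, as an association | – |
| Model for endoscopic findings + MELD | No | Aim 2.3: endoscopic findings as an association; MELD not named |
| 2-year accuracy of each | No | AUC with CI for Aim 1 only |
| Difference with an interval | No | Objectives 3.2.2 and 3.2.3: bleeding only; section 13.2 gives no method for comparing accuracy over time |

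MELD is on both sides, so the contrast is in effect DECT grade + LSN against endoscopic findings.

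**3. How precise the missing estimate would be.** N = 50 is from section 13.1. Assumed, because the documents give none of these: 6 to 20 patients with an event by 2 years, both AUCs A = 0.75, correlation r between the two AUC estimates of 0.5 to 0.85, and complete follow-up.

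Variance = [A(1−A) + (n1−1)(Q1−A²) + (n0−1)(Q2−A²)] / (n1·n0), where Q1 = A/(2−A) = 0.6000, Q2 = 2A²/(1+A) = 0.6429 and A² = 0.5625.

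With 6 events and 44 non-events: [0.1875 + 5 × 0.0375 + 43 × 0.0804] / 264 = 0.01451, so SE = 0.120.

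With equal variances, the half-width of the paired difference is 1.96 × SE × √(2(1−r)):

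| Events | SE | r = 0.5 | r = 0.7 | r = 0.85 |
|---|---|---|---|---|
| 6 | 0.120 | 0.24 | 0.18 | 0.13 |
| 10 | 0.096 | 0.19 | 0.15 | 0.10 |
| 15 | 0.081 | 0.16 | 0.12 | 0.09 |
| 20 | 0.073 | 0.14 | 0.11 | 0.08 |

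This treats the scores as fixed. Censoring and model fitting are not counted.

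**4. Why a non-significant difference would not show equality.** Suppose the comparator AUC is 0.75, the DECT combination is truly 0.65, there are 10 events and r = 0.5. The variances are 0.00915 and 0.01063. SE of the difference = √(0.00915 + 0.01063 − 2 × 0.5 × √(0.00915 × 0.01063)) = 0.0996. The chance of a non-significant result is Φ(1.96 − 0.10/0.0996) − Φ(−1.96 − 0.10/0.0996) = 0.83. Over 5 to 20 events and r = 0.3 to 0.7 it runs from 62% to 91%. Simulated paired DeLong tests (4,000 runs each, score correlation 0.5) gave 84%, 80% and 75% with 5, 10 and 20 events.

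**The case against.** The strongest reply is that the analysis fits the objective. Objective 3.2.4 asks only for prediction from DECT grade, LSN and MELD, and the competing-risks model and cumulative incidence function address those predictors. On this view one sentence in section 13.2 is out of line, in a 50-patient pilot that labels the aim exploratory and claims nothing beyond possible further study. This stands as a limit on severity, and it shows that rewording is part of the remedy. The exploratory label excuses the absence of a formal test and of power. It does not supply an estimate of the quantity hypothesised.

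A second reply is that Aim 2.3 already models endoscopic findings. It does, but as associations, without the endoscopy + MELD combination and without a measure of accuracy.

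Two stronger readings are tempting and not supported:

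- A reader might infer that the investigators will report a DECT association, or a non-significant difference, as proof of equal accuracy. No section says so. The plan leaves that reading open but does not commit to it.
- A reader might put a figure on how often the DECT combination would look equal or better by chance. The documents do not fix the inputs. The answer depends on how far DECT and endoscopic grades disagree, on what LSN adds, and on how many endoscopic findings enter the comparator. Section 11.2 records several besides grade, including red signs, gastric varices and portal gastropathy. Each extra fitted predictor raises apparent accuracy on its own side.

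Nor does the aim call for a non-inferiority margin. With an illustrative margin of 0.10, comparator AUC 0.75, 5 to 20 events and r = 0.3 to 0.7, power at N = 50 would be 9% to 42%, and 80% power would need about 126 to 930 patients.

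**Conclusion.** The concern holds as a mismatch between the Aim 2.4 hypothesis and its analysis. The text alone establishes that the comparison is never estimated; no assumption is needed for that. The sizes do rest on assumptions about event numbers, AUCs and correlation. They show that the added estimate would probably be imprecise, and that neither an association model nor a non-significant difference could support a conclusion of equal or greater accuracy. Because the aim is exploratory and secondary, the point merits correction but does not affect the primary objective or the sample size.

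**What to change.** In section 13.2, amend the Aim 2.4 paragraph as follows:

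1. Reword the hypothesis as estimation: the aim is to estimate the difference in 2-year accuracy between DECT grade + LSN + MELD and endoscopic findings + MELD. State that equal or greater accuracy will not be concluded from the association model or from a non-significant difference.
2. List in advance which endoscopic findings enter the comparator.
3. Fit both combinations in the same patients. Estimate each one's 2-year AUC with a method that handles censoring and competing events.
4. Report the paired difference (DECT side minus endoscopy side), corrected for optimism, with a bootstrap 95% CI that repeats the model fitting in each resample.
5. Keep the association model and cumulative incidence function as description. Set no non-inferiority margin. Add the comparator to objective 3.2.4 so that the sections agree.

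The cost is a few sentences and modest extra analysis. Endoscopic findings, DECT grade, LSN, MELD and 2-year events are already collected under sections 11 and 12, so patients, procedures and sample size do not change. The price is a probably wide interval, which may leave the comparison inconclusive.
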